Safety of repeat injections, comparing incidence of reported AEs from all three studies will be analyzed. Safety will be assessed by monitoring adverse events (AEs) at all study visits. Other safety evaluations are lip function, lip sensation, lip texture, lip firmness, lip symmetry, and lip movement/function.

Other evaluations are Investigator Ease of Use Assessment, Swelling Assessment, and Subject Satisfaction with Lips Assessment.

**Number of Study Centers:** Five (5) sites in the United States

**Duration of Participation:** Subjects will participate in the study for approximately six (6) months from the time they sign the informed consent form (ICF) through the final contact

**Duration of Study:** The study will require approximately 20 months from the beginning to the end of the study (first subject signing the ICF to last contact with last subject)

**Number of Subjects:** Eligible subjects from the PRO 2018-03 study will be encouraged to be retreated during their Day 168/Month 6 telephone call. It is anticipated that the number of subjects will be less than the 158 subjects enrolled in the PRO 2018-02 study.

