# 2 SCHEDULE OF ACTIVITIES

Visit Number (Month)	Visit 1	Phone Contact	Phone Contact	Visit 2 (Mo 1)	Phone Contact	Phone Contact	Unsched Visit
Scheduled Day(s)	Day 1	Day 3	Day 14	Day 28	(Mo 2) Day 56	(Mo 6)  Day 168	
Scheduling Window	± 14 days of Day 168/Month 6 telephone call for PRO 2018-03	·	± 2 days	± 2 days	± 4 days	± 7 days	
Informed consent and AESI Letter	X						
Medical history/ demographics	Xª						
Vital Signs	X						
Vision evaluations (Snellen visual acuity, confrontational visual fields, ocular motility) b	X			X			Xc
Concomitant medication/ Treatment	X	X	X	X	X	X	X
Inclusion/exclusion criteria review	X						
Urine pregnancy test d	X						
Reason for study participation question	X						
Lip Fullness Grading Scale (LFGS) (overall, upper lip, and lower lip)	X			X			X c
Perioral lines at rest severity scale (POL) (overall, upper lip, and lower lip)	X			X			Xc
Lip function	Xe			X			Xc
Lip sensation	Xe			X			Xc
Lip texture	Xe			X			Xc
Lip firmness	Xe			X			Xc
Lip symmetry	Xe			X			Xc
Lip movement/function	X e			X			X c
Patient GAI (pGAI)	Xe			X			Xc
Swelling Assessment	$X^{e}$			X			X c
Investigator GAI (iGAI)	Xe			X			Xc
Subject Satisfaction with Lips	Xe			X			X c
Randomization	X						
Application of Lidocaine cream or inert cream 15 minutes prior to treatment	X						
Treatment with study device	X						
Investigator Ease of Use Assessment	X						
Subject Pain score VAS (immediately after treatment, 15 minutes after treatment)	X						
Subject Pain score VAS				X			X
Treatment question				X			
Adverse event assessment Subject Diary	X Dispense	X	X	X Collect	X	X	X
, ,	F						

Note: The timing of each visit is relative to Day 1, which is defined as the day the subject is treated.

a. To be updated if/as needed for changes since Visit 1 of *PRO 2018-02*.

b. To be performed prior to any treatment and repeated 30 minutes following any treatment and all follow-up visits.

- c. If/as needed
- d. For women of childbearing potential, to be completed prior to enrollment.e. To be performed prior to treatment

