## 7.2 Beginning and End of Study

A subject is considered to be enrolled in the study when he/she has provided written informed consent.

A subject is considered to have completed the study after he/she has completed the Day 168 Month 6/End of study telephone call.

A subject is considered to have withdrawn after he/she has withdrawn consent or has been withdrawn under the conditions specified in Section 7.3.3.

A subject is considered to have been lost to follow-up if he/she cannot be contacted by the investigator. The investigator will document efforts to attempt to reach the subject at least twice by telephone and will send a certified letter before considering the subject lost to follow-up. The end of participation for a subject lost to follow-up is documented as the date of the certified letter.

Each subject will be monitored for the occurrence of AEs, including serious adverse events (SAEs), starting immediately after treatment initiation. Each subject will be followed for safety monitoring until he/she is discharged from the study.

Follow-up procedures related to pregnancy, AEs, or SAEs may continue beyond the end of the study.

Each subject will participate in the study for approximately 6 months from the time he/she signs the ICF through the final contact. After determination of eligibility at Visit 1/Day 1, each subject will be treated with study device.

It is anticipated that the duration of this study will be 20 months from the beginning to the end of the study (first subject signing the ICF to last contact with last subject).

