## 7.3 Study Population

## 7.3.1 Inclusion Criteria

Subjects must meet all of the following criteria to be eligible for the study:

1. Completed Protocol PRO 2018-03

OR

Protocol PRO 2018-02 and did not enroll in Protocol PRO 2018-03.

2. Men or non-pregnant or non-breastfeeding women over 21 years of age

- At PRO 2018-02 baseline visit had an overall score of very thin, or thin on the LFGS, as agreed upon by the Treating and Evaluating Investigators, and desires at least a 1-point improvement in overall LFGS score; OR
  - Had a Fitzpatrick skin phototype IV, V or VI and has an LFGS score of thick or full, as agreed upon by the Treating and Evaluating Investigators, and desires treatment to the vermilion body of 1 or both lips
- 4. If female and of childbearing potential, a negative urine pregnancy test at Visit 1/Day 1 and the subject agrees to use adequate contraception during the study period.
- 5. Willing to give written informed consent and read and sign the Adverse Event of Special Interest (AESI) letter dated 04JUN19.

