#### 7.3.2 Exclusion Criteria

Subjects who meet any of the following criteria will be excluded from the study:

- 1. Women who are pregnant, lactating, or planning a pregnancy.
- 2. Subjects with a known history of allergy, anaphylaxis or hypersensitivity to injectable hyaluronic acid products, local anesthetics of the amide type such as lidocaine, or to latex.
- 3. Subjects with a significant ongoing adverse event from PRO 2018-02 or PRO 2018-03 that in the opinion of the investigator could be worsened by participation in this study.
- 4. Subjects that experienced an SAE, AESI, visual changes or other serious medical conditions during PRO 2018-02 or PRO 2018-03.
- 5. Subjects with abnormal vision evaluations (Confrontational Visual Fields, Ocular Motility) or abnormal Snellen Visual Acuity at Visit 1 pre-treatment as defined in section 7.6.5 and Appendix 5.
- 6. Subjects who are unable to withhold thrombolytics, or inhibitors of platelet aggregation or nonsteroidal anti-inflammatory drugs (NSAIDs, e.g., aspirin, ibuprofen) or other substances known to increase coagulation time (e.g., herbal supplements with garlic or gingko) within 10 days before AND after any injection session.
- 7. Subjects with clinically significant organic disease including clinically significant cardiovascular, hepatic, pulmonary, neurologic, or renal disease or other medical condition, serious intercurrent illness, or extenuating circumstance that, in the opinion of the investigator, preclude participation in the trial.
- 8. Subjects with lip tattoos, piercings, facial hair, or scars that would interfere with visualization of the lips and perioral area for the effectiveness assessments.
- 9. Subjects with abnormal lip function, with inability to effectively sip water through a straw.
- 10. Subjects with abnormal lip sensation with inability to feel a 0.4G monofilament or a cotton wisp at any site on the lip.
- 11. Subjects with moderate or severe abnormal lip asymmetry.

- 12. Subjects with any mass formation on the lip.
- 13. Subjects with dentures or any device covering all or part of the upper palate, and/or severe malocclusion or dentofacial or maxillofacial deformities as judged by the Treating Investigator. Subjects planning to undergo extensive dental procedures such as dental implants, multiple tooth extractions, or oral surgery should not participate. Minor dental procedures such as teeth cleaning and repair of caries are not exclusionary.

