## 7.4.5 Method of Packaging, Labeling, Storage, and Dispensing

For PN40082, one 1.0 mL syringe is packaged along with two fine-gauge needles (30G) in an easy-open tray. Each syringe is equipped with a Luer-Lok as well as a custom finger grip and plunger rod. The syringes contain a peelable label to be placed on the subject record for tracking purposes. Two trays are packaged in a carton. A label that includes the protocol number and Sponsor name will be attached to each carton.

For RV001 with topical anesthetic, one 1.0 mL syringe is packaged along with two fine-gauge needles (27G) in an easy-open tray. 30G fine-gauge needles will be provided in bulk by the Sponsor for use instead of the 27G needles. Each syringe is equipped with a Luer-Lok as well as a custom finger grip and plunger rod. The syringes contain a peelable label to be placed on the subject record for tracking purposes. Two trays are packaged in a carton. A label that includes the protocol number and Sponsor name will be attached to each carton. Bulk commercial supplies of LMX4 will be provided.

For RV001, one 1.0 mL syringe is packaged along with two fine-gauge needles (27G) in an easy-open tray. 30G fine-gauge needles will be provided in bulk by the Sponsor for use instead of the 27G needles. Each syringe is equipped with a Luer-Lok as well as a custom finger grip and plunger rod. The syringes contain a peelable label to be placed on the subject record for tracking purposes. Two trays are packaged in a carton. A label that includes the protocol number and Sponsor name will be attached to each carton. To confirm use of the 30G needles, the 27G needles should remain in the retained packaging for reconciliation.

All study device will be stored in a climate-controlled, limited access area.

The investigator agrees to store and administer the study device only at the site(s) listed on Form FDA 1572 (or investigator agreement/statement). The investigator, sub-investigator(s), or qualified designees also agree that the study device will be administered only to subjects who have provided written informed consent and have met all entry criteria. The study device may not be used for any purpose other than as stated in the protocol.

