### 7.5 Study Schedule

The visit-by-visit schedule of study activities is provided in Section 2. The timing of each visit is relative to Day 1, which is defined as the day the subject is treated in PRO 2019-02.

All visits should be performed within the windows specified on the schedule of study activities. Every attempt should be made to have each subject attend each visit as scheduled. If a subject is unable to attend a visit within the specified window the visit should be scheduled as closely as possible to the applicable window.

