## 7.7.1 Visit 1/Day 1: Treatment

Visit is  $\pm 14$  days of Day 168/Month 6 telephone call for PRO 2018-03 or for subjects enrolled from PRO 2018-02, Visit 1 is Day 1.

- Obtain written informed consent and read and sign the AESI letter dated 04JUN19.
- Update the medical history and demographic information as needed from entry to Protocol PRO 2018-02 and PRO 2018-03
- Perform vital signs (temperature, heart rate, blood pressure, and respiratory rate)
- Vision evaluation (Snellen visual acuity, confrontational visual fields, ocular motility)
- Obtain/record concomitant medications/treatments

- Evaluate inclusion/exclusion criteria
- Perform urine pregnancy test for all women of childbearing potential
- Reason for study participation question
- LFGS assessment
- POL assessment
- Lip function evaluation prior to treatment administration
- Lip sensation evaluation prior to treatment administration
- Lip texture evaluation prior to treatment administration
- Lip firmness evaluation prior to treatment administration
- Lip symmetry evaluation prior to treatment administration
- Lip movement/function prior to treatment administration
- pGAI assessment prior to treatment administration
- iGAI assessment prior to treatment administration
- Swelling assessment prior to treatment administration
- Subject satisfaction with lips (VAS) prior to treatment administration
- Treatment administration waiting 15 minutes after lidocaine cream or inert cream application
- Investigator Ease of Use assessment
- Subject Pain Score immediately after treatment (VAS)
- Subject Pain Score 15 minutes after treatment (VAS)
- Vision evaluation (Snellen visual acuity, confrontational visual fields, ocular motility) 30 minutes post treatment.
- Assess AEs
- Dispense subject diary card
- Schedule next visit
- Complete CRFs

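### The Visit 1 window allows re-injection up to 14 days before the PRO 2018-03 Month 6 call, which fits poorly with the requirement that PRO 2018-03 be completed

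*Combined protocol and SAP*

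**What the plan says.** The timing rule for roll-over subjects appears twice. The Schedule of Activities (Section 2) places Visit 1 within plus or minus "14 days of Day 168/Month 6 telephone call for PRO 2018-03". Section 7.7.1 repeats this and adds a separate arrangement for direct entrants: "telephone call for PRO 2018-03 or for subjects enrolled from PRO 2018-02, Visit 1 is Day 1". Neither place limits the visit to on or after the call.

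Visit 1 is the injection visit. Section 7.5 counts all visits from "Day 1, which is defined as the day the subject is treated in PRO 2019-02".

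Eligibility is stated separately. Inclusion 1 (Section 7.3.1) reads "Completed Protocol PRO 2018-03", or, as the alternative, PRO 2018-02 without enrolment in PRO 2018-03. Section 7.4.5 has the investigator agree that "the study device will be administered only to subjects who have provided written informed consent and have met all entry criteria".

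Two other places bear on what completion means. On recruitment, the synopsis says: "Eligible subjects from the PRO 2018-03 study will be encouraged to be retreated during their Day 168/Month 6 telephone call". For the present study, Section 7.2 says: "A subject is considered to have completed the study after he/she has completed the Day 168 Month 6/End of study telephone call". The document does not define completion of PRO 2018-03.

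**The concern.** The anchor is a contact that belongs to the preceding study, and the window extends to both sides of it. A site that follows the schedule alone may inject before that contact. A site that follows inclusion 1 may have to wait for it. The two rules agree only on and after the call, unless completion of PRO 2018-03 falls earlier than the call.

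Two things depend on the order of events. First, exclusion 3 bars "Subjects with a significant ongoing adverse event from PRO 2018-02 or PRO 2018-03" that participation could worsen, and exclusion 4 bars anyone who had a serious event, an event of special interest, visual changes or another serious condition in the earlier studies. Both are best judged once PRO 2018-03 safety reporting has closed. Second, the synopsis says that adverse event incidence will be compared across all three studies. If two follow-up periods run together, a reaction to the new injection could be recorded under the old study.

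**Working it through.** No sample size, power or error rate is involved. The check is a comparison of rules plus day counts.

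**Inputs**
- Window: −14 to +14 days around the PRO 2018-03 Day 168/Month 6 call (Sections 2 and 7.7.1).
- Injection day: Day 1 of PRO 2019-02 (Section 7.5).
- Diary: 2 weeks after treatment, i.e. 14 days (Section 7.6.25).
- Window of the PRO 2018-03 call: not given. Assumption where needed: ±7 days, as for this study's own Day 168 call.

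**Step 1. What completion could mean**
- *Reading A: completion is the call.* Section 7.2 defines it so for this study, and the synopsis places the invitation to retreatment in the PRO 2018-03 call. Both point this way; neither proves it. A Visit 1 before the call then cannot satisfy inclusion 1.
- *Reading B: completion is earlier.* This cannot be ruled out. The present protocol attaches an end-of-study label to both its Month 1 visit and its Month 6 call, and only Section 7.2 settles which one counts. Injection before the call is then permitted.

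**Step 2. Day counts if the anchor is the actual call**
- Window length: 14 + 1 + 14 = 29 days.
- Before the call: 14 days. Call day onward: 15 days.
- Under A, 14/29 = 48% of the days are barred by inclusion 1, and compliant conduct gives no overlap.
- Under B, injection *d* days before the call (*d* = 1 to 14) puts the call on PRO 2019-02 Day *d* + 1. Overlap is up to *d* days, provided that PRO 2018-03 still collects adverse events until its call. At *d* = 14 the call falls on Day 15 and the overlap is 14 days, the length of the diary period.

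**Step 3. Day counts if the anchor is scheduled Day 168**

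Visit 1 may then fall on PRO 2018-03 Day 168 − 14 = 154 to Day 168 + 14 = 182. With the actual call on Day *c*, the days before it are *c* − 154:

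| Actual call (±7 days assumed) | Days before call = maximum overlap | Share of 29 days |
|---|---|---|
| Day 161 | 161 − 154 = 7 | 24% |
| Day 168 | 168 − 154 = 14 | 48% |
| Day 175 | 175 − 154 = 21 | 72% |

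The 48% and 14-day figures therefore hold for the actual-call anchor, or for a call made exactly on Day 168. The text does not say which anchor applies.

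**Step 4. Size in subjects**

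The document gives no input for how many roll-over subjects would be injected before their call. No share of subjects and no change in adverse event incidence can be calculated.

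**The case against.** The strongest reply is that a visit window is a scheduling tolerance and does not override eligibility. Sections 7.2 and 7.7.1 have eligibility determined at Visit 1 before treatment, and Section 7.4.5 bars use of the device otherwise. The window and inclusion 1 can both be met on the call day and the 14 days after it, and the recruitment route in the synopsis leads there. If the anchor is scheduled Day 168 and the call came early, some days before Day 168 are already after the call and have a legitimate use. This largely stands. Under Reading A, a site that respects inclusion 1 makes no error. What remains is that the schedule offers days which eligibility forbids, and does not say what it is anchored to.

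The harms are also small. Before injection, Visit 1 includes an in-person history update, medication review, vision testing and lip examinations, so an excluding event would have to be missed there and then surface by telephone. Onset dates are recorded and subject numbers carry over, so events can be assigned by date. Section 8 leaves data-handling conventions to the SAP, so the absence of an assignment rule from the protocol is not a defect in itself.

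A reader might infer more: that ineligible subjects will be treated, that about half of the window is unusable, or that the three-study adverse event comparison is biased. The document supports none of these. The first requires either a deviation or an unseen definition, the second depends on the anchor, and the third needs overlap in actual subjects and double or wrong listing under PRO 2018-03 rules that are not available.

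**Conclusion.** The point holds as a minor inconsistency in a stated rule. On the likelier reading, the pre-call part of the window conflicts with inclusion 1. On the other, re-injection can come before the last PRO 2018-03 safety contact, with up to 14 days of overlapping follow-up when the window is counted from the actual call (7 to 21 days at most if counted from scheduled Day 168, with the assumed ±7-day call window). Which reading applies depends on the PRO 2018-03 protocol, which was not available.

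The number of subjects affected may be zero, and no effect on adverse event incidence is claimed. Randomized comparisons within PRO 2019-02, including pain scores, are unaffected, as are subjects entering directly from PRO 2018-02.

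**What to change.** In Section 2 and Section 7.7.1, for subjects coming from PRO 2018-03, set Visit 1 at 0 to +14 days after the completed PRO 2018-03 Day 168/Month 6 call, with the same day allowed provided that the call comes first. This fixes the anchor, removes the conflict under Reading A and the overlap under Reading B, and means exclusions 3 and 4 are judged after the last PRO 2018-03 contact.

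The cost is a wording change in two places and the loss of the pre-call scheduling days, which inclusion 1 probably rules out already. Counted from the actual call, sites keep 15 of 29 days.

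Optionally, the SAP could state that for any subject already injected before the call, events with onset at or after the PRO 2019-02 injection count only under PRO 2019-02 in the three-study comparison.

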## 7.7.2 Telephone Contacts on Day 3 and Day 14 ( $\pm$ 2 days)

- Assess AEs
- Assess concomitant medications/treatments
- Ask whether the subject is experiencing or has experienced any signs/symptoms of vision changes or stroke since the injection
- Confirm adherence to prohibited treatments/medications

## 7.7.3 Visit 2/Day 28 (± 2 days): Month 1 End of Study Visit

- Vision evaluation (Snellen visual acuity, confrontational visual fields, ocular motility)
- Assess concomitant medications/treatments
- LFGS assessment
- POL assessment
- Lip function evaluation
- Lip sensation evaluation
- Lip texture evaluation
- Lip firmness evaluation
- Lip symmetry evaluation
- Lip movement/function
- pGAI assessment
- iGAI assessment
- Swelling assessment
- Subject satisfaction with lips (VAS)
- Subject Pain Score (VAS)
- Assess AEs
- Treatment Question
- Collect/Review subject diary card
- Complete CRFs

## 7.7.4 Telephone Contact on Day 56 (Month 2) $\pm$ 4 days

- Assess AEs
- Assess concomitant medications/treatments
- Ask whether the subject is experiencing or has experienced any signs/symptoms of vision changes or stroke since the injection
- Confirm adherence to prohibited treatments/medications

## 7.7.5 End of Study Telephone Contact on Day 168 (Month 6) $\pm$ 7 days

- Assess AEs
- Assess concomitant medications/treatments
- Ask whether the subject is experiencing or has experienced any signs/symptoms of vision changes or stroke since the injection

• Confirm adherence to prohibited treatments/medications

#### 7.7.6 Unscheduled Visit

An unscheduled visit is allowed at any time if in the investigator's opinion it is warranted. The following procedures may be performed at the Unscheduled Visit if required.

- Vision evaluation (Snellen visual acuity, confrontational visual fields, ocular motility)
- Assess concomitant medications/treatments
- LFGS assessment
- POL assessment
- Lip function evaluation
- Lip sensation evaluation
- Lip texture evaluation
- Lip firmness evaluation
- Lip symmetry evaluation
- Lip movement/function
- pGAI assessment
- iGAI assessment
- Swelling assessment
- Subject satisfaction with lips (VAS)
- Subject Pain score (VAS)
- Assess AEs
- Complete CRFs

### 7.8 Efficacy Endpoints

Efficacy will be evaluated by the Subject Pain Score immediately after treatment, 15 minutes after treatment, and at Visit 2. Efficacy will also be evaluated by LFGS, POL, pGAI, iGAI, and Swelling Assessment.

## 7.9 Assessment of Safety

## 7.9.1 Safety Endpoints

Safety of the treatment with PN40082 or RV001 with topical anesthetic, or RV001 will be evaluated by the nature, severity, and frequency of treatment-emergent adverse events (TEAEs). All AEs that occur during the study will be recorded whether or not they are considered to be related to treatment. A description of the AE will be recorded with the date of onset, date of resolution, severity of the AE, relationship to the study device, action taken, and the outcome. The frequency and type of AEs will be evaluated for each group based on the previous

treatments that they received in the PRO 2018-02 and PRO 2018-03 protocols, and the difference in AEs in this protocol (PRO 2019-02) between the subjects who received injections that contained lidocaine, and the group that was treated with topical lidocaine.

